5.2.2. Analyses for Categorical Endpoints

Categorical endpoints and relevant safety endpoints will be presented using summary statistics: number of observations, counts and percentages.

5.2.3. Longitudinal Analysis using Mixed Model Repeated Measures (MMRM) model

MMRM models will include the change from baseline of the relevant endpoints as specified in [Section 6](#) as the dependent variable and will include treatment, baseline, day, baseline*day interaction and the day*treatment interaction, with day fitted as a repeated effect, and participant as a random effect.

An unstructured covariance matrix will be used to estimate the variances and covariance within participant across time points. If convergence is not obtained or model fit is not adequate then other covariance structures (eg CS) will be investigated as necessary. The

Kenward-Roger approximation will be used for estimating degrees of freedom for the model parameters. Missing values will be imputed as part of the MMRM model assumptions.

The Least Squares Means (LSMeans) together with 90% confidence intervals and standard errors will be obtained for each treatment and day. Differences in LSMean between each treatment and placebo, together with 90% confidence intervals and standard errors, will also be obtained.

Standard SAS output will be provided to support the main statistical summary table for the models.

5.2.4. Analysis of Covariance (Raw Scale)

The ANCOVA model will include the change from baseline of the relevant endpoint as specified in [Section 6](#) as the dependent variable and will include treatment as a fixed effect and baseline as a covariate.

Missing values will not be imputed.

The Least Squares Means (LSMeans) together with 90% confidence intervals and standard errors will be obtained for each treatment. Differences in LSMean between each treatment and placebo, together with 90% confidence intervals and standard errors, will also be obtained.

Standard SAS output will be provided to support the main statistical summary table for the models.

Example SAS code is provided in the [Appendices](#).

5.2.5. Analysis of Covariance (Log Scale)

The ANCOVA model will include the natural logarithmic transformed of relative change from baseline of the relevant endpoint as specified in [Section 6](#) as the dependent variable and will include treatment as a fixed effect and log(baseline) as a covariate.

Missing values will not be imputed.

The adjusted geometric Least Squares Means (LSMeans) together with 90% confidence intervals and standard errors will be obtained for each treatment. Differences in adjusted geometric LSMean between each treatment and placebo, together with 90% confidence intervals and standard errors, will also be obtained.

Standard SAS output will be provided to support the main statistical summary table for the models.

Example SAS code is provided in the [Appendices](#).

5.2.6. Cumulative Incidence Plots

Cumulative Incidence Plots will be produced based on the time to the event of interest (starting from the time of start of dosing on Day 1) for each treatment group separately and will be plotted on the same graph. This will be based on plotting the cumulative incidence function (with no competing risks), which will be presented as a % on the y-axis. No statistical testing for differences between treatment groups will be considered.

Details of censoring are included in [Section 6.2.1.2](#) and example SAS code is provided in the [Appendices](#).

5.3. Methods to Manage Missing Data

For the analysis of safety endpoints, the sponsor data standard rules for imputation will be applied.

5.3.1. Pharmacokinetic Concentrations Below the Limit of Quantification

In all data presentations (except listings), concentrations below the limit of quantification (BLQ) will be set to zero. (In listings BLQ values will be reported as “<LLQ”, where LLQ will be replaced with the value for the lower limit of quantification.)

5.3.2. Deviations, Missing Concentrations and Anomalous Values

In summary tables and plots of median profiles, statistics will be calculated having set concentrations to missing if 1 of the following cases is true:

1. A concentration has been collected as ND (ie, not done) or NS (ie, no sample),
2. A deviation in sampling time is of sufficient concern or a concentration has been flagged anomalous by the pharmacokineticist/clinical team.

Note that summary statistics will not be presented at a particular time point if more than 50% of the data are missing.

5.3.3. Pharmacokinetic Parameters

Actual PK sampling times will be used in the derivation of PK parameters.

If a PK parameter cannot be derived from a participant’s concentration data, the parameter will be coded as NC (ie, not calculated). Note that NC values will not be generated beyond the day that a participant discontinues.

In summary tables, statistics will be calculated by setting NC values to missing; and statistics will be presented for a particular dose with ≥ 3 evaluable measurements.

If a participant receives a dose that was not assigned based on the randomized titration scheme (for example due to a down-titration), the PK data from that Day will not be included in the calculation of summary statistics but will be included in listings.

If an individual participant has a known biased estimate of a PK parameter (due for example to an unexpected event such as vomiting before all the compound is adequately absorbed in the body), this will be footnoted in summary tables and will not be included in the calculation of summary statistics or statistical analyses.

5.3.4. 4- β -hydroxycholesterol/cholesterol ratio

Rules described in [Section 5.3](#) will be used to manage concentrations below limit of quantification, deviations, missing concentrations and anomalous values.

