### 2.2.2.1. Clinical Safety

Clinical data for the completed study, C3991001, are provided in the current version of the IB.

A blinded summary of currently available data from study C3991002 is provided below. These data should be considered preliminary and subject to update on final reporting of the study's results. PF-07081532 or matching placebo have been administered to a total of 51 participants with T2DM and 15 participants with obesity. A dose titration approach was used, where doses within a cohort were titrated up to a target dose over the dosing period. The duration of titration varied across cohorts. The target doses ranged from 10 mg (no titration phase) to 180 mg PF-07081532 or matching placebo. Each cohort was expected to receive study drug at the target dose level for a minimum stable dosing period of 7 days.

Four cohorts of participants with T2DM have been randomized to receive doses of PF-07081532 (target doses of 10 mg to 120 mg) or matching placebo once daily for 28 days. One cohort of 10 participants with T2DM has been randomized to receive PF-07081532 titrated to a target dose of 180 mg, or matching placebo, once daily for 42 days. One cohort of 15 participants with obesity has been randomized to receive PF-07081532 titrated to a target dose of 180 mg or matching placebo once daily for 42 days. One participant who completed dosing (blinded target dose 30 mg/placebo) experienced an SAE of acute gallstone pancreatitis during the follow-up period. The investigator reported that there was a reasonable possibility that the event was related to blinded study drug. The totality of available data, including medical history, has been reviewed by the Sponsor. The overall evidence, in the opinion of Sponsor, points to gallstone, rather than drug-induced pancreatitis, as the likely cause of this event. There was no change to the benefit/risk profile of PF-07081532, nor was any change to the conduct of the ongoing clinical study judged to be required.

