**Figure 1. Sample Dosing Scheme**

If a participant does not tolerate dose increment to the next dose level, as determined by the investigator and with notification to the sponsor, the participant may be reverted to the previously tolerated dose level. Following this dose modification, 2 separate attempts at increasing the dose to the next dose level are permitted, per investigator discretion. If, per investigator assessment, unacceptable intolerance (eg, severe vomiting) occurs shortly following dose administration, the dose will not be re-administered on the same day, and the participant may resume dosing at the current dose level at the next scheduled dosing time. Participants whose dose level is tolerability-limited may continue in the study for the intended duration of their assigned cohort at their own individual MTD, as judged to be appropriate by the PI and sponsor.

The planned cohorts in the study (Cohorts 1-3) may be conducted concurrently, partially overlapping or sequentially. The sponsor may decide not to conduct all planned cohorts, if it is judged that study objectives have been met. Up to 3 additional cohorts may be enrolled if judged necessary to meet the study objectives. One or more of the study cohorts may be conducted in non-diabetic participants with obesity, see [Section 4.2.1](#) and [Section 5](#).

Determination of eligibility will occur within 28 days of randomization based on criteria including medical history, vital sign, ECG and laboratory parameters, as detailed in [Section 5](#). Participants deemed eligible will be admitted to the CRU 7 days prior to start of dosing (Day -7) and will remain on-site until at least Day 45, post first dose.

The treatment period with double-blind study intervention will be 42 days, with study drug administered once daily. The participants within a given cohort will be blinded to the study treatment (PF-07081532 versus placebo). Participants who discontinue prior to completion of the study may be replaced, at the discretion of the PI and sponsor.

Upon discharge from the CRU, participants will return to the CRU 7 to 14 days after the last administration of IP for an on-site follow-up visit. A further follow-up contact with participants will be conducted at least 28 days and up to 35 days after the last administration of IP; this contact may be done via a phone call.

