6.3. Secondary Endpoint(s)

6.3.1. PF-07081532 PK Parameters

- Estimand strategy: Not applicable
- Analysis set: PF-07081532 Concentration and Pharmacokinetic Parameter Set

To assess the pharmacokinetics of PF-07081532, the PK parameters detailed in [Section 3.2](#) will be listed and summarized for participants in the PK analysis set (as defined in [Section 4](#)). Missing values will be handled as detailed in [Section 5.3](#) along with handling of values where participants received a dose that was not assigned based on the titration scheme). Each PK parameter will be summarized by treatment (eg differentiating different doses and dosing frequencies as required), and Study Day (Day 1, and 42, as applicable).

The parameters will include the set of summary statistics as specified in the table below:

Table 3. PF-07081532 PK Parameters to be Summarized Descriptively

Parameter	Matrix	Summary Statistics
AUC ₂₄ , AUC ₂₄ (dn), C _{max} , C _{max} (dn), PTR, R _{ac} , C _{av} , C _{min} , R _{ac,Cmax} , , CL/F, Vz/F, AUC _{inf} , AUC _{last}	Plasma	N, arithmetic mean, median, cv%, standard deviation, minimum, maximum, geometric mean and geometric cv%.
T _{max}	Plasma	N, median, minimum, maximum.

$t_{1/2}$	Plasma	N, arithmetic mean, median, cv%, standard deviation, minimum, maximum.
-----------	--------	--

There will be one summary table presenting all PK parameters. The treatment subheading will include the analyte, matrix, dose information and day (Day 1, or Day 42). As per [Section 5.3.3](#), data collected on days that participants received anything other than the assigned dose based on the titration scheme will only be listed and not summarized as part of the summary table.

To assess the relationship between the PK parameters and dose for PF-07081532, dose normalized AUC_{24} and C_{max} will be plotted against treatment (using a logarithmic scale) for Day 1, and Day 42 separately and will include individual participant values and the geometric means for each dose. Geometric means will have a different symbol than the individual values. The values will be dose normalized (to a 1 mg dose) by dividing the individual values and raw geometric means by dose. A footnote will be added to the plots to indicate that geometric means are presented.

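### The Day 42 PK rule checks only the dose taken that day, so a participant re-escalated on Day 41 or 42 can be summarised at the assigned dose before reaching steady state

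*SAP*

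**What the plan says.** SAP 5.3.3 handles down-titration with a rule tied to the single day. If the dose taken was not the one assigned by the randomised titration scheme, "the PK data from that Day will not be included in the calculation of summary statistics but will be included in listings". SAP 6.3.1 applies the same rule to the PK summary table: "data collected on days that participants received anything other than the assigned dose based on the titration scheme will only be listed and not summarized". Neither section asks how long the participant had been on the assigned dose.

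The next paragraph of SAP 5.3.3 adds a general clause, which opens "If an individual participant has a known biased estimate of a PK parameter (due for example to an unexpected event such as vomiting". Such an estimate is footnoted and left out of summaries and analyses.

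Protocol 4.1 (text under Figure 1) says that a participant who does not tolerate an increment "the participant may be reverted to the previously tolerated dose level". It continues: "Following this dose modification, 2 separate attempts at increasing the dose to the next dose level are permitted, per investigator discretion". It gives no last day for an attempt. Under Protocol 4.3, Cohort 1 takes 20 mg for 28 days and 60 mg for the remaining 14, so the upper level covers Days 29 to 42.

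Protocol Table 5 makes Day 42 AUC24 and Cmax secondary endpoints. It labels the Day 42 value as steady state in the formulas for Rac and Rac,Cmax and derives CL/F as dose divided by AUC24. Those three parameters are exploratory.

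**The concern.** A plasma profile on Day 42 reflects the doses of the preceding days as well as that morning's dose. A participant who returned to the higher level on Day 41 or 42 still carries a profile built partly on the lower dose, yet passes a rule that looks only at Day 42. The value is then summarised under the assigned dose.

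The error runs one way. AUC24, Cmax, their dose-normalised forms, Rac and Rac,Cmax come out too low and CL/F too high. It falls on participants who tolerated the increment poorly, in a study meant to inform later titration schemes (Protocol 4.2 and 4.3). The affected values also feed the dose-normalised plots and the accumulation-ratio analysis of variance with 90% confidence intervals in SAP 6.3.1.

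**Working it through.** The documents give no figure to reproduce: the sample size is empirical (Protocol 9.5), and no human half-life is readable in the public text. The size of the effect therefore rests on an assumed half-life, shown over a range.

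**Inputs**
- Dose step: 20 to 60 mg once daily (Protocol 4.3), a ratio of 20/60 = 1/3.
- Active participants per cohort: 9 (Protocol 9.5).
- Half-life t: assumed, 8 to 48 h.
- n: consecutive assigned doses up to and including Day 42. Return on Day 42 is n = 1, on Day 41 n = 2, on Day 40 n = 3.

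**Formula.** Linear one-compartment superposition, with the lower dose at steady state before the return:

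f(n) = Day 42 AUC24 / steady-state AUC24 at 60 mg = 1 − (1 − 1/3) × 2^(−24n/t)

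Example with t = 24 h and n = 2: 1 − 0.667 × 0.25 = 0.833.

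| Half-life (assumed) | n = 1 (Day 42) | n = 2 (Day 41) | n = 3 (Day 40) | n = 7 | n = 14 |
|---|---|---|---|---|---|
| 8 h | 0.917 | 0.990 | 0.999 | 1.000 | 1.000 |
| 12 h | 0.833 | 0.958 | 0.990 | 1.000 | 1.000 |
| 24 h | 0.667 | 0.833 | 0.917 | 0.995 | 1.000 |
| 36 h | 0.580 | 0.735 | 0.833 | 0.974 | 0.999 |
| 48 h | 0.529 | 0.667 | 0.764 | 0.941 | 0.995 |

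A numerical oral model (absorption rate constant assumed to be 1 per hour) agreed to within about 0.01 for AUC24, and Cmax moved the same way.

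**Derived parameters for the affected participant.** Rac falls by the same fraction as AUC24. CL/F is multiplied by 1/f: at 12, 24 and 36 h by 1.20, 1.50 and 1.72 for a Day 42 return, and by 1.04, 1.20 and 1.36 for a Day 41 return. In this linear model the terminal half-life does not change and Tmax barely does.

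**Cohort geometric mean, 1 of 9 affected:** the factor is f^(1/9).
- Day 42 return: 0.980, 0.956 and 0.941 at 12, 24 and 36 h, a fall of 2.0%, 4.4% and 5.9%.
- Day 41 return: 0.995, 0.980 and 0.966, a fall of 0.5%, 2.0% and 3.4%.

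**Where it starts to matter.** Setting f = 0.90 and solving for t, an individual shortfall above 10% needs a half-life over about 8.8 h for a Day 42 return, 17.5 h for Day 41 and 26 h for Day 40.

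**Participants who follow the scheme.** With the planned 14 days at 60 mg, f is at least 0.995 throughout this range, so the problem is confined to late returns.

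**The case against.** The strongest reply is that SAP 5.3.3 already covers this. Exclusion under the biased-estimate clause is mandatory once bias is known, vomiting is given only as an example, and dose dates and times are in the CRF (Protocol 6.4), so a late re-escalation can be recognised. That stands in part: the rules do not force every such profile into the summary. But the clause's one example is an unexpected event, whereas re-escalation is permitted by design, and the clause sets no dosing-history criterion. The specific rule for down-titration is day-only. In a sponsor-open study with unblinded data reviews (Protocol 9.4), a stated criterion is better than case-by-case recognition.

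Three stronger readings are tempting and should be resisted:
- **That the secondary PK endpoints as a whole are biased.** They are defined as Day 1 and Day 42 values, with no steady-state label. Only AUC24 and Cmax move.
- **That the cohort summary could be off by as much as 17%.** That needs 3 of 9 participants all returning on Day 42 itself, with a 36 h half-life (0.580^(3/9) = 0.834). Nothing in the documents suggests this pattern.
- **That seven days is an established PK rule of the programme.** Protocol 2.2.2.1 says of the previous multiple-dose study: "Each cohort was expected to receive study drug at the target dose level for a minimum stable dosing period of 7 days". That is an expectation about dosing. Requiring seven days at the Day 42 dose could also remove a whole cohort if a later scheme's last step is shorter, since step durations may be adjusted.

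It is also fair that these summaries are mainly descriptive, no hypothesis is tested, and the listings and individual profiles would still show an affected participant.

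**Conclusion.** The concern holds in a limited form. The day-only rule admits profiles that still carry over from a lower dose, and the neighbouring clause narrows the gap without closing it. The effect can be large for the individual and is modest for the cohort: with 1 of 9 affected and a half-life of 12 to 36 h, the geometric mean falls about 2-6% for a Day 42 return and 0.5-3.4% for a Day 41 return. At a half-life of about 8 h or less, a Day 41 return costs the individual 1% or less.

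These figures assume linear one-compartment kinetics, a 20 to 60 mg step and steady state at the lower dose before the return; a brief reversion would leave a smaller shortfall. How many participants will return late is unknown. The correction is cheap and worth making before the data are summarised.

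**What to change.** In SAP 5.3.3 and 6.3.1, summarise Day 42 AUC24, Cmax and the parameters derived from them (the dose-normalised values, Cav, PTR, CL/F, Vz/F, Rac and Rac,Cmax) only for participants who took the dose that the titration scheme assigned on each day of a prespecified window ending on Day 42. List the others with their dosing history. Equivalently, state that a deviation from the scheme within that window counts as a known biased estimate.

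Set the window from the half-life the sponsor knows, for example about 5 half-lives. For the 20 to 60 mg step this leaves AUC24 at 1 − 0.667/32 = 0.979 of steady state. A 7-day window gives at least 97% for half-lives up to 36 h and 94% at 48 h. Defining the window by adherence to the scheme, and not by days at one dose level, keeps a cohort whose last scheduled step is short.

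The cost is a sentence in each section and a flag built from dosing records already in the CRF. The downside is that a few participants may move from summary to listing. With 9 active participants per cohort and a minimum of 3 evaluable values for a summary, the table should state how many were moved. No change to dosing is implied.

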5.3.5. Pharmacodynamic Parameters

For baseline AUC₀₋₄ calculations, if participants have a missing baseline (ie, Day -1) 0 hour value, no imputation will be made. No imputation will be made for other missing values.

AUC₀₋₄ will only be calculated in any participant with at least the first, last, and 75% of the total number of samples within the given interval available. Nominal times will be used in the calculation. No imputation for missing values will be conducted for these PD endpoints.

If the concentrations are below the limits of quantification such values will be truncated at the limit of quantification for all summaries and analyses, and will appear as reported in all listings.

The same principles apply to the analyses of all other PD endpoints.

6. ANALYSES AND SUMMARIES

Data collected before baseline will only be listed , unless otherwise stated.

In case of additional cohorts with non-diabetic participants with obesity, for all relevant analyses, the placebo arm will be presented as two separate treatment groups for the T2DM participants and non-diabetic participants with obesity.

6.1. Baseline Variables

Not applicable

6.2. Primary Endpoint

6.2.1. Safety Analysis

- Estimand strategy: Not applicable
- Analysis set: Safety set

A set of summary tables split by treatment will be produced to evaluate any potential risk associated with the safety and toleration of administering PF-07081532.

No formal analyses are planned for safety data. The safety and other endpoints detailed in [Section 3.1](#) will be listed and summarized in accordance with sponsor reporting standards, Disposition of Subjects

Subject evaluation groups will show end of study subject disposition. Frequency counts will be supplied for subject discontinuation(s) by treatment.

Data will be reported in accordance with the sponsor reporting standards.

6.2.1.1. Demographic and Physical Examination Data

A breakdown of demographic data will be provided for age, gender, race, and ethnicity (T2DM and non-diabetic obesity, summarized separately). The physical measurement - height; weight; body mass index; duration of T2DM (for T2DM participants only) - at baseline will also be summarized. Each will be summarized by treatment and 'All Subjects' in accordance with the sponsor reporting standards.

An additional table listing the screening data of free T4, TSH, calcitonin, amylase, lipase, C-peptide and HbA1c will be produced as above.

6.2.1.2. Discontinuation(s)

Subject discontinuations, temporary discontinuations or dose reductions due to adverse events will be detailed and summarized by treatment.

Data will be reported in accordance with the sponsor reporting standards.

6.2.1.3. Adverse Events

Adverse events will be reported in accordance with the sponsor reporting standards.

Incidence and severity of treatment emergent adverse event (TEAE) tables will additionally be produced ('All causality' and 'Treatment related', separately) to summarise the total number of adverse events by preferred term, which will be reported by treatment group and overall.

A set of individual profile plots will be produced separately for each TEAE of interest. Each plot will include horizontal bars by participant which will represent if/when a participant experienced the TEAE of interest (measured in days). The x-axis will represent time and the bars will be colored by severity, with the plots paged by treatment group. Multiple events for the same participant of the same TEAE would therefore be represented by multiple horizontal bars.

Time to the first occurrence of TEAEs of interest will be produced using Cumulative Incidence Plots as described in [Section 5.2.6](#). Participants who discontinue from the study, discontinue from IP will be censored at the discontinuation/initiation date.

A separate plot for each TEAE will be produced separately.

The above will also be produced separately for the time to the first recurrence of the TEAEs of interest. There will be a separate line for each treatment group.

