## **7. DISCONTINUATION OF STUDY INTERVENTION AND PARTICIPANT DISCONTINUATION/WITHDRAWAL**

### **7.1. Discontinuation of Study Intervention**

It may be necessary for a participant to permanently discontinue study intervention. Reasons for permanent discontinuation of study intervention include the following: ECG changes, adverse events, laboratory abnormalities, potential cases of acute kidney injury or taking of prohibited medications, as described below.

Note that discontinuation of study intervention does not represent withdrawal from the study. If study intervention is permanently discontinued, the participant will remain in the study to be evaluated for safety and PK, if possible. See the [SoA](#) for data to be collected at the time of discontinuation of study intervention and follow-up for any further evaluations that need to be completed.

In the event of discontinuation of study intervention, it must be documented on the appropriate CRF/in the medical records whether the participant is discontinuing further receipt of study intervention or also from study procedures, posttreatment study follow-up, and/or future collection of additional information.

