3.1.1. Adverse Events

An adverse event is considered treatment emergent (TEAE) relative to a given treatment if:

- the event starts during the effective duration of treatment (i.e. starting after or on the first dose but before the last dose plus lag time)

The effective duration of treatment is determined by the lag time. Any event occurring within the lag time, whether this occurs during a break in treatment or at the end of treatment, is attributed to the corresponding treatment period. The lag time is defined by the Pfizer Standard of 365 days post last dose of IP.

Adverse events occurring up to the first dose of active treatment on Day 1 will be considered non-treatment emergent.

A 3-tier approach for summarizing AEs will not be used for this study as there is a low number of subjects planned to be enrolled per treatment group, although risk differences and related summaries for AEs of interest will be presented as defined in 3.4.1.1.

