3.4. Other Safety Endpoints

3.4.1.1. Adverse events of interest

The TEAEs of interest for additional reporting are: nausea, vomiting and diarrhoea (as defined based on preferred term). Based on emerging blinded data reviews, other AEs of interest may be added to this list, which would be documented with a SAP amendment or documented in the changes to planned analysis section in the CSR.

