8. REFERENCES

3. ICH Harmonised Guideline E9 (R1); Estimands and Sensitivity Analysis in Clinical Trials; 16 June 2017.
4. Pfizer Guidance for Evaluation of QT / QTc Interval Prolongation and Proarrhythmic Potential for Non-antiarrhythmic Drugs; Members of the Cardiovascular Safety & Advisory Council (CVSAC); January 26, 2018.

APPENDICES**Appendix 1. Statistical Methodology Details**Example SAS code for MMRM Model:

```
proc mixed data = dataset method=reml;
    class subject treatment time;
    model cfb = treatment base time base*time time*treatment / ddfm=kr residual
outp=resid_out;
    repeated time /subject=subjid type = un;
    lsmeans treatment*time/diff cl alpha=0.1;
    ods output lsmeans=lsmeans_out;
    ods output diffs=diffs_out;
run;
```

Example SAS code for Cumulative Incidence Plots:

```
proc lifetest data = dataset method=km plots=cif(test) outcif=cifatrisk intervals=0 to 20 by 2;
    strata treatment;
    time day*censor(1)/eventcode=0;
run;
```

NOTE: the censor variable has a value = 1 when the related time is censored and has a value = 0 when the event of interest occurs. There should be no other values available for this censored variable in this dataset (including missing values). If required, missing observations should be removed prior to analysis.

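### The cumulative-incidence plots for nausea, vomiting and diarrhoea censor at IP discontinuation as if stopping were non-informative, so the plotted percentage can differ from the TEAE tables

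*SAP*

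**What the plan says.** **The plots.** SAP 3.4.1.1 names the events: "The TEAEs of interest for additional reporting are: nausea, vomiting and diarrhoea (as defined based on preferred term". SAP 5.2.6 describes the method as "plotting the cumulative incidence function (with no competing risks", with time running from the start of dosing on Day 1, one curve per treatment group and no between-group testing. The example code in SAP Appendix 1 reads "time day*censor(1)/eventcode=0", where 1 means censored and 0 means event. The note beneath it says: "There should be no other values available for this censored variable in this dataset (including missing values". Stopping IP can therefore be coded only as ordinary censoring.

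**The censoring rule.** SAP 6.2.1.3 states: "Participants who discontinue from the study, discontinue from IP will be censored at the discontinuation/initiation date". The time-to-first-recurrence plots are produced in the same way. SAP 5.2.6 refers the reader to Section 6.2.1.2 for censoring details, but that section covers discontinuation summaries and contains no censoring rule.

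**What counts as a TEAE.** SAP 3.1.1 states: "The lag time is defined by the Pfizer Standard of 365 days post last dose of IP".

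**What happens after IP is stopped.**
- Protocol 7.1: "If study intervention is permanently discontinued, the participant will remain in the study to be evaluated for safety and PK, if possible".
- Protocol 7.2.1 keeps in follow-up those who ask to stop IP.
- Protocol 8.3.1 collects AEs for at least 28 days after the last dose, ending early only if consent is withdrawn (or at screen failure).
- Protocol 4.1 places the last contact 28 to 35 days after the last dose.
- Protocol 7.1.2 goes the other way: participants stopped for a treatment-related SAE, or at discretion for another serious or severe AE, are also withdrawn from the study.

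**The concern.** Protocol 4.2 gives the purpose as judging the tolerability of different starting doses and titration increments, because gastrointestinal effects are the expected problem. The three plotted symptoms are those effects, and these plots are the only group-level time-to-event curves planned for them.

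Two things follow from censoring at IP discontinuation. First, the tables and the curves both claim to show TEAEs but use different windows, so the same event can be in one and not in the other. Second, with no competing event the estimator is one minus Kaplan-Meier. It assigns to someone who stopped the later risk of those who carried on. A participant who stops because of nausea is thus treated, in the vomiting and diarrhoea plots, as exchangeable with people who tolerated the drug. In Cohort 1 that later risk includes the step from 20 mg to 60 mg after Day 28 (Protocol 4.3), which an earlier stopper never received. A reader who takes the plotted percentage as the proportion of dosed participants who vomited would be misled.

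**Working it through.** **1. Is there a figure to reproduce?** No. Protocol 9.5 sets the cohort size empirically at 9 active and 3 placebo (9 + 3 = 12). Neither document states an event rate or a stopping rate, so every count below other than 9 is an assumption.

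**2. One participant, traced through the rules.** Suppose someone has nausea, stops IP for it on Day 10, and on Day 14 vomits for the first time and has nausea again.
- First-nausea plot: counted, because the event precedes the censoring.
- First-vomiting plot: censored at Day 10, so the vomiting is not shown.
- Nausea-recurrence plot: censored at Day 10, so the recurrence is not shown.
- TEAE table: both Day 14 events count. They fall 4 days after the last dose, inside the 28-day collection period and inside the lag time.

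The effect therefore falls on the symptoms that did not cause the stop and on the recurrence plots. In an active group of 9, each first event missed in this way is 1/9 = 11.1 points of crude incidence.

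**3. Group percentages.** Assume 9 active participants, *m* of whom stop event-free before the dose step, and 3 events afterwards among the other 9 − *m*.
- Plot: 1 − (6 − *m*)/(9 − *m*) = 3/(9 − *m*)
- Table, no stopper has the event later: 3/9
- Table, every stopper has it later: (3 + *m*)/9

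| *m* | Plot | Table, none later | Table, all later |
|---|---|---|---|
| 1 | 3/8 = 37.5% | 33.3% | 4/9 = 44.4% |
| 2 | 3/7 = 42.9% | 33.3% | 5/9 = 55.6% |
| 3 | 3/6 = 50.0% | 33.3% | 6/9 = 66.7% |

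If IP discontinuation were a competing event, the on-treatment cumulative incidence would be 3/9 = 33.3% in every row. The planned curve is thus neither the all-follow-up incidence nor the on-treatment incidence.

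**4. The order of events matters.**
- First events on Days 3, 5, 8 and 30, two event-free stops on Day 10: the plot is 1 − (8/9)(7/8)(6/7)(3/4) = 50.0%. The table reads 4/9 = 44.4%, 5/9 = 55.6% or 6/9 = 66.7% if 0, 1 or 2 stoppers have a later first event.
- Three events, all before the two stops: the plot is 33.3%. The table reads 33.3%, 44.4% or 55.6%.

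**5. Direction.** A simulation of 400,000 participants assumed an on-drug event hazard of 0.5 per 42 days and a stopping hazard of 0.25 per 42 days, so that about 14% to 18% stop event-free. The shared propensity is a gamma frailty with variance 1.

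| Propensity shared by event and stopping | Off-drug risk | Plot | Actual in-study | If nobody stopped |
|---|---|---|---|---|
| Yes | none | 31.3% | 28.7% | 33.5% |
| Yes | same as on drug | 31.2% | 33.4% | 33.4% |
| No | none | 39.4% | 35.2% | 39.4% |
| No | same as on drug | 39.3% | 39.3% | 39.3% |

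The curve can be too high or too low against what happens in the study. When stopping and events share a cause, it also misses the incidence that would be seen if nobody stopped, which is the quantity that non-informative censoring is meant to recover.

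**The case against.** The case for leaving the rule alone has real content.

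- *Censoring at IP stop is an on-treatment display.* That is a reasonable thing to want when judging titration steps. But the plot is not labelled on-treatment, and one minus Kaplan-Meier with stopping censored does not estimate on-treatment incidence (step 3).
- *Few may stop.* Protocol 4.1 lets intolerant participants return to a tolerated dose and continue; they stay on IP and are not censored. If nobody stops, there is no numerical effect. With two stoppers and no later events the gap is 42.9 − 33.3, about 9.5 points, which is less than one participant of nine. This limits the size but does not remove the mismatch.
- *The plots are descriptive.* No test or decision rule depends on them, and the TEAE tables remain. This stands.

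A reader might also infer more than the documents support:

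- *That these plots are the only time-resolved display of GI tolerability.* They are not. SAP 6.2.1.3 also plans individual profile plots over time, coloured by severity, with no such censoring stated. AE-related discontinuations and dose reductions are summarised as well.
- *That everyone who stops stays in the study.* Protocol 7.1.2 withdraws some, so this is the general rule and not a universal one.
- *That completers' post-dose events are kept while stoppers' are cut.* The SAP does not say when completers are censored. What can be said is that their cut-off is missing.
- *That the curve overstates risk, or distorts active drug only.* Neither document gives stopping rates by arm or off-drug risk, so no direction can be claimed.

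**Conclusion.** The point holds as a mismatch between stated rules. The curves stop counting at IP discontinuation, the TEAE definition does not, and most participants who stop remain under AE collection. With stopping coded as plain censoring, intolerance-driven stopping is taken to be unrelated to later nausea, vomiting or diarrhoea, which is implausible for these symptoms.

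The numerical range in step 3 rests on assumed stopping counts and on all three events following the stops. It shows what could happen and is not a forecast. The consequence is a group-level curve that can be misread beside the tables for the primary tolerability objective; no error rate is affected. It is worth correcting because the data needed are already collected.

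Two drafting faults add to it: the censoring sentence mentions an *initiation* date although no initiating event is defined, and the cross-reference in SAP 5.2.6 is wrong.

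**What to change.** In SAP 6.2.1.3, choose one of the following and say which:

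1. **All-follow-up curve.** Follow every dosed participant to the end of active AE collection, that is, the last AE contact, about 28 to 35 days after the last dose. Censor only at loss of AE follow-up or study withdrawal. Do not use the 365-day lag as the cut-off, since active collection ends long before it.
2. **On-treatment curve.** Code IP discontinuation as a competing event, using a third status value in the same PROC LIFETEST call. Amend SAP 5.2.6 and the Appendix 1 note to allow this, apply one stated cut-off to completers and stoppers alike, and label the plot on-treatment.

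In either case:
- The sponsor should clarify what *initiation* refers to. The sentence may have lost a listed item, so deleting the word could remove an intended censoring event.
- Correct the SAP 5.2.6 cross-reference from 6.2.1.2 to 6.2.1.3.
- Reconcile Protocol 7.1 with 7.1.2 on who remains in the study after stopping, since this decides whose later events can be observed.

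The cost is a few words in three places of the SAP and one recoded status variable, with no new data. The downside of option 1 is that the curve includes some off-drug time, as the TEAE tables already do. It also leaves some early censoring if an early stopper's last contact comes 28 days after their own last dose, so the number at risk should be shown.
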